6.8 Ensuring adequate resources

To conduct a sound and valid study the investigators will ensure to the best of their ability that the following criteria are met:

- 1) Reasonable potential to recruit 1110 individuals to the study over a cumulative 9-month period.
- 2) An appropriate amount of time to complete recruitment, intervention, and data collection (9 months).
- 3) An adequate supply of suitably qualified staff at each facility including:
 - a) Appointed research nurse at each research site able to carry out the following responsibilities 3 days per week:
 - 08:00 to 10:00
 - Checking National Health Laboratory Services Results (NHLs) for blood tests at outpatient clinic
 - Telephonic follow-up with recruited patients to discontinue iron supplementation if they do not meet criteria for IDA
 - 10:00 to 16:00
 - Recruitment of patients for study
 - Obtaining written informed consent and assent where appropriate
 - Performing finger-prick Hb (Hemacue)
 - Applying EMLA for venepuncture for anaemic patients

Giving drug script signed by clinic doctor for oral iron supplementation ± deworming medication for collection at the hospital pharmacy

- b) Appointed research assistant for all sites to complete weekly telephonic survey for all IDA patients assessing medical adherence and side-effects, referring onto study nurse or doctor where appropriate.
- 3) Appropriate training on the study protocol, about any investigational product and about their duties to allow the staff to carry out their tasks safely and effectively.
- 4) Appropriate supervision of any individual or group to whom the investigator assigns trial-related duties at the trial site
- 5) Assurance that any person or party retained to perform trial-related duties is suitably qualified to perform those duties.

6.9 Criteria for iron deficiency

The patient will be allocated to iron-deficiency group if they meet one or more of the following criteria.

- 1. Serum Ferritin WHO Definitions³¹
- 2. Transferrin saturation (TSAT) <11%³²

6.10 Supplemental iron dosing regimen

All patients diagnosed with anaemia on the point of care Hemacue test will be given an oral iron supplement to take every day prior to surgery for a maximum of 3 months.

The recommended treatment dose of elemental iron for IDA is $3-6\text{mg}^{-1}\text{kg}^{-1}\text{day}^{-1}$ ³³. This can be increased to $12\text{mg}^{-1}\text{kg}^{-1}\text{day}^{-1}$. The recommendation from Red Cross War Memorial Hospital Pharmacy is that iron syrup is preferred in children up to 4 years old or in older children unable to take tablets (Table 1).

Table 1. Ferrous gluconate (350mg/5ml) Elemental Iron 8mg/ml Dosing

Weight (kg)	BD dose (mL)
5	2
6	2.5
7	2.5
8	3
9	3.5
10	4
11	4
12	4.5

13	5
14	5.5
15	5.5
16	6
17	6.5
18	7
19	7
20	7.5

If the child can take iron tablets the recommendation is possible to prescribe a dose at increments of $\frac{1}{2}$ tablet (37.5mg) (Table 2).

Table 2: Ferrous Fumarate/Folic acid - Elemental iron 65mg tablets Dosing

Weight Range	Tablets*
10 to 14 kg	1.0
>15 to 20 kg	1.5
>20 to 30 kg	2.0
>30kg	3.0

*Dose to be split into BD

Table 3: Ferrous sulphate - Elemental iron 55mg tablets Dosing

Weight Range	Dose
20 to < 27 kg	1 tab bd
27 to < 37 kg	2 tab am/1 tab pm
37 kg and above	2 tab bd

Based on this the dose range when prescribing tablets for patient weight range 10 to 59 kg is 2.2 to $6.5 \text{ mg}^{-1}\text{kg}^{-1}\text{day}^{-1}$. The oral iron supplementation will be dispensed the same day as the outpatient clinic appointment, with clear verbal instructions on how to take the medication and potential side-effects. The parent or legal guardian will also be given a patient information leaflet, with information on anaemia, how to take the medication, potential side-effects, and who to contact should they have any further questions or concerns (Appendix D).

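### Section 6.10 contradicts its own tablet figures: the half-tablet iron content and the lower end of the stated dose range do not follow from the tables, and Table 2 as printed has no row above 14 kg and up to 15 kg

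*Combined protocol and SAP*

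**What the plan says.** Everything needed is in section 6.10 (Supplemental iron dosing regimen).

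- The text allows tablets in half-tablet steps, gives the iron content of a half, and refers the reader to the second table: "tablet (37.5mg) (Table 2").
- Table 2 is headed "Ferrous Fumarate/Folic acid - Elemental iron 65mg tablets Dosing". Its rows are 10 to 14 kg (1.0 tablet), >15 to 20 kg (1.5), >20 to 30 kg (2.0) and >30 kg (3.0). The footnote, "Dose to be split into BD", makes these daily totals.
- Table 3 is headed "Ferrous sulphate - Elemental iron 55mg tablets Dosing". It gives 1 tablet twice daily from 20 to below 27 kg, 2 in the morning and 1 in the evening from 27 to below 37 kg, and 2 twice daily from 37 kg.
- After the tables comes the summary: "Based on this the dose range when prescribing tablets for patient weight range 10 to 59 kg is 2.2 to" 6.5 mg/kg/day.

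Section 6.13 lists the prescribed elemental iron dose per kg per day as a recorded variable for all anaemic patients.

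**The concern.** The half-tablet figure, the table headings, the tablet counts and the summary range all describe one regimen, so each should follow from the others. Two do not, and the weight bands do not join up.

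This is operative text for treating children at several hospitals. Under section 6.8 the research nurse's duties include "Giving drug script signed by clinic doctor for oral iron supplementation", and section 6.10 adds: "The oral iron supplementation will be dispensed the same day as the outpatient clinic appointment". There is therefore little time to query a discrepancy before iron is given. Three things are at stake: whether the protocol describes its own regimen correctly, whether the dose entered under section 6.13 is calculated in the same way everywhere, and whether every child in the claimed weight range has a row to read from.

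**Working it through.** **Inputs**, all from section 6.10: 65 mg per tablet (Table 2 heading), 55 mg per tablet (Table 3 heading), the tablet counts and weight bands listed above, the stated half tablet of 37.5 mg, and the stated range of 2.2 to 6.5 mg/kg/day for 10 to 59 kg.

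**Formula.** Daily dose per kg = tablets per day × mg per tablet / weight. The top band of each table is cut at 59 kg, the upper weight in the plan's own sentence.

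**1. The stated range**

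| Table | Band (kg) | mg/day | mg/kg/day at lower limit | mg/kg/day at upper limit |
|---|---|---|---|---|
| 2 | 10 to 14 | 1.0 × 65 = 65 | 65/10 = 6.50 | 65/14 = 4.64 |
| 2 | >15 to 20 | 1.5 × 65 = 97.5 | just under 97.5/15 = 6.50 | 97.5/20 = 4.88 |
| 2 | >20 to 30 | 2.0 × 65 = 130 | just under 130/20 = 6.50 | 130/30 = 4.33 |
| 2 | >30 to 59 | 3.0 × 65 = 195 | just under 195/30 = 6.50 | 195/59 = 3.31 |
| 3 | 20 to <27 | 2 × 55 = 110 | 110/20 = 5.50 | just over 110/27 = 4.07 |
| 3 | 27 to <37 | 3 × 55 = 165 | 165/27 = 6.11 | just over 165/37 = 4.46 |
| 3 | 37 to 59 | 4 × 55 = 220 | 220/37 = 5.95 | 220/59 = 3.73 |

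The plan's upper end of 6.5 is reproduced. Its lower end of 2.2 is not: the minimum is 3.31 in Table 2 and 3.73 in Table 3, so the result is the same whichever table the sentence refers to. The discrepancy is 3.31/2.2 = 1.5-fold. With the printed counts, 2.2 would be reached only at 195/2.2 = 88.6 kg (Table 2) or 220/2.2 = 100 kg (Table 3), both outside the stated weight range.

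**2. The half tablet**

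- Table 2: 65/2 = 32.5 mg. Table 3: 55/2 = 27.5 mg. Neither is 37.5 mg.
- 37.5 mg implies a tablet of 2 × 37.5 = 75 mg, which is in neither table. One such tablet at 10 kg would give 75/10 = 7.5 mg/kg/day, above the stated maximum of 6.5.
- Overstatement if a half of the 65 mg tablet is counted at 37.5 mg: 37.5/32.5 = 1.154, or 15.4%. This upper limit is reached where a dose is made up only of halves, for example 1.0 tablet split into two halves (75 against 65 mg/day). Table 3 uses whole tablets only, so the question does not arise there.

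**3. The weight bands**

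- Table 2 as printed includes 14 kg in its first row and starts its second row above 15 kg. Weights above 14 kg and up to and including 15 kg fall in neither.
- Table 3 starts at 20 kg. Table 1 lists 14 and 15 kg, but for syrup only. The summary sentence nevertheless claims tablet dosing from 10 to 59 kg.

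**The case against.** The strongest reply is that tablets are prescribed by count within a weight band. A prescriber reading Table 2 needs no conversion to mg, a tablet contains the same iron whatever the text says, and the range sentence summarises the tables without being a prescribing rule. That stands. A reader might infer that children would receive a different dose because of the 37.5 mg or the 2.2; the documents do not support this.

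Other replies also carry weight:

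- Both table headings print mg per tablet, sites must have an on-site pharmacy (section 6.4), and staff training is required (section 6.8). A wrong conversion in the recorded dose is therefore possible rather than expected. The outpatient form and iron leaflets (Appendices E and I) are listed but not shown, so a correct conversion may be printed there.
- A reader might infer that 2.2 comes from a superseded scheme with two tablets for the heaviest children, since 2 × 65/59 = 2.20. That is conjecture: 2 × 55/50 = 2.20 and 65/30 = 2.17 come as close, and the documents do not say how 2.2 was obtained.
- A reader might infer underdosing because 2.2 lies below the 3 to 6 mg/kg/day that follows "The recommended treatment dose of elemental iron for IDA is". The printed tablet doses do not show that: from 10 to 59 kg every one exceeds 3. Some also exceed 6, and the same paragraph allows an increase to 12.
- The gap in the bands may be smaller than it looks. If a comparison sign was lost in PDF reading, 15 kg itself is covered; if weights are also rounded to whole kilograms, as Table 1 lists them, nothing is left uncovered. Both conditions are assumptions, and rounding alone would still leave 15 kg without a row.
- 37.5 differs from 32.5 by one digit, so a typing or reading error is possible. This cannot be checked from the text available.

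None of this makes the half-tablet figure or the lower end of the range agree with the printed tables.

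**Conclusion.** Section 6.10 contradicts its own figures in two places and has an apparent omission in a third. The half tablet is stated as 37.5 mg against 32.5 or 27.5 mg from the headings. The range starts at 2.2 mg/kg/day against 3.31 or 3.73 from the tables. Table 2 as printed has no row above 14 kg and up to 15 kg.

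The consequences are limited. The range misdescribes the regimen, and the dose recorded under section 6.13 could be overstated by up to 15% for the 65 mg tablet if the text's half-tablet figure is used. Only the missing row leaves a prescriber without an answer; the documents do not give the number of tablet-taking children it concerns.

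A reader might infer that the efficacy result is at risk. It is not: section 5.11 names duration of iron treatment but no analysis by dose, and neither the paired haemoglobin comparison nor the sample size and power calculations use these figures.

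The arithmetic assumes that Table 2 counts are daily totals, as its footnote indicates, and that the headings and counts were read correctly from the PDF. The third item is the least certain, for the reasons given above. The section should be corrected before use.

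**What to change.** The sponsor should reconcile the half-tablet content, tablet strengths, tablet counts, weight bands and stated range in section 6.10. The half-tablet figure and the mg/kg/day range should then be restated from the reconciled tables, and the same mg per tablet used for the dose recorded under section 6.13. Which values are right, and how the weight bands should read, is for the clinical team and pharmacy to decide.

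The cost is a correction to one section and a check that the outpatient case record form and the iron leaflets use the same mg per tablet. No extra data or patients are needed.

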6.11 Empiric treatment for worms

If the patient has not been dewormed in the last 6 months, they will be administered deworming medication in the surgical out-patient clinic as per the Standard Treatment Guidelines and Essential

6.12 Research procedures, data collection and collation

At recruitment phase

Eligible patients will be screened for anaemia with a finger-prick bedside Hemacue test at outpatient clinic. If the patient meets the WHO criteria for anaemia EMLA cream will be applied to potential sites for venepuncture and the patient will then be sent to the pathology laboratory for venepuncture with a request form for tests that will include laboratory full blood count (FBC), ferritin, transferrin saturation (TSAT), C-reactive protein (CRP), and reticulocyte Hb content. Patients who have not been dewormed within the last 6 months will be treated with mebendazole or albendazole as per the South African guidelines³³.

The patients age, weight, height, co-morbidities, ASA physical status, planned surgical procedure, planned date of surgery, severity of surgery, and type of surgery will be recorded. They will also be informed that they will be contacted telephonically once a week by the research assistant to enquire about compliance with the medication and enquire about any side-effects with the medication. The telephonic contact details will be confirmed by the research nurse and documented on the paper Outpatient CRF.

At home

The laboratory blood test results will be reviewed within 48 hours to diagnose those patients who meet the criteria for IDA. Any patients who do not meet the criteria will be contacted via telephone by the research nurse to instruct them to stop taking the iron supplementation and to bring the remaining iron supplementation with them to their next hospital visit. These patient folders and results for those patients not meeting the criteria for IDA will be reviewed by the appropriate surgical team to decide on appropriate ongoing management and further investigations which will be individualised to the patient.

For those patients meeting the criteria for IDA and continuing the oral iron supplementation, the parent or legal guardian will be contacted weekly to complete a short telephonic survey on compliance with the medication, side-effects, and to answer any questions or concerns they may have.

At time of Surgery

Repeat laboratory FBC at time of routine preoperative bloods if part of standard care.

Repeat ferritin, CRP, TSAT ± FBC whilst under anaesthesia prior to start of surgery.

Data collection

Each individual hospital will collect and record data on a paper case record form (CRF) for every patient recruited. These include an Outpatient Clinic CRF (Appendix E), Telephonic Survey CRF (Appendix F), and Surgical Admission CRF (Appendix G). The Outpatient Clinic CRF and the Surgical Admission CRF will be kept in a booklet in the patient folder and a sticker will be placed on the folder to identify that the patient has been recruited. All the CRFs, including the Telephonic Survey CRF will be kept in a secure study file in a locked cupboard.

Data will be anonymised by generation of a unique study code and transcribed by local investigators onto a secure, password protected internet based electronic CRF in the REDCap platform. Each patient will only be identified on the electronic CRF by their numeric code; thus, the co-ordinating study team cannot trace data back to an individual patient without contact with the local team. A participant (patient) list will be used in each hospital to match identifier codes in the database to individual patients to record clinical outcomes and supply any missing data points. Access to the data entry system will be protected by username and password delivered during the registration process for individual local investigators. All electronic data transfer between participating hospitals and the co-ordinating centre will be encrypted using a secure protocol (HTTPS/SSL 3.0 or better).

Each hospital will maintain a secure study file including a protocol, local investigator delegation log, ethics approval documentation, the participant list, and other additional documentation such as study definitions.

A final summary printout of included patients with major variables should be produced for each hospital together with final data submission to double check for completeness and accuracy.

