A recent Cochrane review on the role of preoperative iron in reducing perioperative blood transfusion in adult patients found no significant reduction in the administration of allogeneic blood transfusion in patients who had received preoperative iron compared with those who did not¹⁰. These findings were supported by the Preoperative intravenous iron to treat anaemia before major abdominal surgery (PREVENTT) trial which found no difference in blood transfusion or death between the patients who did and did not receive intravenous iron¹¹. However, these findings have generated much discussion in the literature and concerns have been raised about the clinical application of this study. The mean Hb difference between the two groups post intervention (0.47g.dL⁻¹) highlights the need for greater understanding of the impact of an intervention on the absolute or relative increase in Hb when designing trials looking at the impact of iron treatment on perioperative outcomes. Dosing regimens of preoperative oral iron varies widely between studies further complicating the ability to draw conclusions of the role of oral iron in the treatment of preoperative anaemia¹²⁻¹⁶.

In contrast with the findings of the Cochrane review and the PREVENTT trial, a meta-analysis of patient blood management programme (PBM) studies, many of which include preoperative iron treatment as a component, found that there was a reduction in exposure to red cell transfusions¹⁷. Although, the meta-analysis also found the implementation of PBM was not associated with a reduction on in-hospital mortality or 30-day mortality, there was no additive benefit from multiple interventions and no trial showed that PBM were cost-effective.

Not included in this meta-analysis were recently published studies on the implementation of preoperative anaemia screening clinics in adults in elective colorectal surgery and major surgery which demonstrated reductions in red cell transfusions^{18,19}, length of stay^{18,19}, and net costs¹⁸ in patients with IDA who were treated with preoperative intravenous iron. Similarly, a large study from Western Australia reported significant reductions in cost associated with the use of blood products, and improved patient outcomes, after implementation of a PBM²⁰.

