Studies investigating the impact of increasing preoperative haemoglobin on perioperative outcomes in children are primarily focused on blood loss and blood transfusion rates in surgery in which significant bleeding and frequent blood transfusion are anticipated and most children in these studies received preoperative erythropoietin²¹⁻²⁷. The impact of preoperative oral iron as a stand-alone intervention to increases preoperative Hb are limited to 2 studies^{28,29}. A single retrospective study has reported on the impact of the introduction of preoperative oral iron without EPO in children undergoing spinal surgery²⁸. They found a significant difference in intraoperative transfusion rates in patients who received a longer duration of preoperative oral iron therapy. The major limitation of the study was a lack of preintervention Hb, precluding the ability to assess the effect of iron supplementation on delta Hb.

A subsequent study reviewing the impact of preoperative oral iron in paediatric cardiac patients found that iron supplementation resulted in an increase in preoperative haemoglobin levels which was associated with reduced red blood cell transfusion volumes²⁹.

Given the high incidence of preoperative anaemia in children having surgery in South Africa in the public sector and its association with poorer postoperative outcomes, it is important to assess the feasibility of a pragmatic intervention to treat preoperative anaemia in the context of a resource-constrained setting. Although intravenous iron in combination with EPO may be more effective and have fewer side effects, oral iron is relatively inexpensive and widely available in South Africa. Regular deworming may also play an important role in the treatment of preoperative anaemia and has been shown to be an effective intervention to increase baseline Hb in school age children from low- and middle- income countries³⁰.

We hypothesise that the implementation of preoperative anaemia screening and treatment of anaemic patients with a minimum of 6 weeks supplementation with oral iron will have a clinically significant effect on increasing the haemoglobin in patients with preoperative IDA.

4. Study objectives

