5.2 Primary outcome measure

DHb (pre-intervention Hb – post-intervention Hb)

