6.13 Dataset

A realistic data set will be fundamental to the success of the investigation. This dataset will include the following:

All patients:

- Age (continuous, numerical)
- Sex (categorical, nominal)
- Weight (continuous, numerical)
- Height (continuous, numerical)
- Co-morbidities (categorical, nominal)
- Chronic medication (categorical, nominal)
- ASA Physical Status (categorical, ordinal)
- Severity of surgery (categorical, nominal)
- Type of surgery (categorical, nominal)
- Hemacue Hb

All anaemic patients

- Pre-intervention Hb (continuous, numerical)

- Pre-intervention MCV (continuous, numerical)
- Pre-intervention ferritin (continuous, numerical)
- Pre-intervention TSAT (continuous, numerical)
- Pre-intervention CRP (continuous, numerical)
- Pre-intervention reticulocyte Hb content (continuous, numerical)
- Syrup or tablet prescribed (categorical, nominal)
- Actual dose of elemental iron prescribed ($\text{mg}^{-1} \cdot \text{kg}^{-1} \cdot \text{day}^{-1}$)

All patients with IDA

- Post-intervention Hb (continuous, numerical)
- Post-intervention MCV (continuous, numerical)
- Post-intervention ferritin (continuous, numerical)
- Post-intervention TSAT (continuous, numerical)
- Post-intervention CRP (continuous, numerical)
- Post-intervention reticulocyte Hb content (continuous, numerical)
- Days of oral iron treatment (continuous, numerical)

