6.15 Collection and storage of blood samples

EMLA will be applied by the research nurse at the outpatient clinic. These patients will then have venepuncture performed by the on-site hospital phlebotomist. These samples will include an EDTA tube for FBC, and reticulocyte Hb content, and a gold top tube (serum separator) for C-reactive protein, ferritin, and transferrin saturation content. These samples will be labelled and stored in accordance with standard operating procedure.

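### The source of the post-iron Hb, and any fluid given before it is drawn, are neither fixed nor recorded, so dilution could shrink DHb by an unknown amount in an unknown share of children

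*Combined protocol and SAP*

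**What the plan says.** The primary outcome (section 5.2) is a within-child difference, "DHb (pre-intervention Hb – post-intervention Hb"), so a rise in Hb gives a negative value. Section 6.1 describes a quasi-experimental pre-post design, and no control group is planned.

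**Baseline sample.** Anaemic children have EMLA cream applied in the outpatient clinic and are then bled: "These patients will then have venepuncture performed by the on-site hospital phlebotomist" (section 6.15). That the child is awake is implied, not stated.

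**Post-iron sample.** Section 6.12 gives two possible sources:
- The first depends on local practice: "Repeat laboratory FBC at time of routine preoperative bloods if part of standard care".
- The second is the study's own draw in theatre: "Repeat ferritin, CRP, TSAT ± FBC whilst under anaesthesia prior to start of surgery".

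The second limits the draw relative to surgery but not relative to intravenous fluid. Its FBC is optional, and the protocol does not say when the option applies or which result is the endpoint if a child has both.

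**Recording and analysis.** The dataset in section 6.13 has a single entry, "Post-intervention Hb (continuous, numerical"), with nothing listed for source, time of draw or fluid already given. Section 5.11 plans a paired t-test or a rank test, and a mixed model adjusting for baseline Hb. None has a term for sampling condition.

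**Effect size.** The hypothesis is that the programme "will have a clinically significant effect on increasing the haemoglobin in patients with preoperative IDA", with no target in g/dL. The Introduction says that an earlier trial's result "highlights the need for greater understanding of the impact of an intervention on the absolute or relative increase in Hb" when such trials are designed.

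**The concern.** Intravenous fluid lowers Hb concentration without changing red-cell mass. If some post-iron samples are drawn after fluid and no baseline sample is, the difference between the two contains a dilution component that opposes the iron effect. A control group sampled in the same way would carry the same component, and it would cancel in the comparison. Here there is none, so it passes directly into DHb.

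Which children are affected is unlikely to be random. Those without routine preoperative bloods can have a post-iron Hb only from theatre, and who has routine bloods may depend on the type of surgery and the hospital. One variable would then mix two measurement conditions.

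What is at stake is mainly the estimated size of the Hb rise, which the Introduction says trials need to know. If the true rise is modest, the significance test is at stake too.

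**Working it through.** **1. The plan's own figures.** A paired t-test with 176 pairs, 80% power and two-sided 0.05 gives a detectable effect of 0.2123 SD (the plan states 0.2123609). For 35, 53, 70 and 88 pairs the results are 0.49, 0.39, 0.34 and 0.30, matching the power table. For the 44 children with IDA expected in the section 6.7 site table, it is 0.43 SD. The plan gives no SD in g/dL. If the SD of change is 0.8-1.5 g/dL (assumed), 0.43 SD is 0.35-0.65 g/dL.

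**2. Fall in Hb from dilution.** Every input is an assumption: Hb 10 g/dL, blood volume 75 mL/kg, fluid V mL/kg, and fraction f still in the circulation at the draw.

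Fall = 10 × [1 − 75/(75 + V × f)]

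| V (mL/kg) | f = 0.25 | f = 0.50 | f = 0.75 |
|---|---|---|---|
| 0 | 0 | 0 | 0 |
| 5 | 0.16 | 0.32 | 0.48 |
| 10 | 0.32 | 0.62 | 0.91 |

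For example, V = 5 and f = 0.25 gives 10 × (1 − 75/76.25) = 0.16 g/dL. With wider assumptions (Hb 8-11 g/dL, blood volume 70-80 mL/kg, f 0.25-1.0) the ranges are 0.12-0.73 g/dL at 5 mL/kg and 0.24-1.38 g/dL at 10 mL/kg.

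**3. Bias in mean DHb.** Bias = q × fall, where q is the share of children whose Hb comes from the theatre draw after fluid. The documents do not give q.

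| Fluid | q = 25% | q = 50% | q = 100% |
|---|---|---|---|
| none | 0 | 0 | 0 |
| 5 mL/kg | 0.04-0.12 | 0.08-0.24 | 0.16-0.48 |
| 10 mL/kg | 0.08-0.23 | 0.16-0.45 | 0.32-0.91 |

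**4. A yardstick.** The only Hb difference in g/dL that the protocol quotes is "The mean Hb difference between the two groups post intervention (0.47g.dL⁻¹"), from an adult intravenous-iron trial. At the central assumptions, the retained fluid that lowers Hb by this amount is 75 × 0.47/(10 − 0.47) = 3.7 mL/kg.

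**5. Effect on the test.** Take n = 44 and an assumed SD of change of 1.0 g/dL. The mean observed rise is the true rise − q × fall, and its SD is √[1 + q(1 − q) × fall²]. Power is the noncentral-t probability of a significant rise.

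| True rise | Fall | q = 25% | q = 50% | q = 100% |
|---|---|---|---|---|
| 0.47 | 0 | 86% | 86% | 86% |
| 0.47 | 0.30 | 72% | 54% | 20% |
| 0.47 | 0.47 | 61% | 32% | 2.5% |
| 1.0 | 0.47 | >99% | >99% | 93% |

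In the last cell the test survives, but the observed mean rise is 1.0 − 0.47 = 0.53 g/dL, about half the true value.

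**The case against.** **Not all post-iron Hb is drawn under anaesthesia.** A reader of the theatre line alone might infer that it is. The documents do not support this: the FBC there is optional, and the preceding line provides a routine preoperative FBC where that is standard care. A natural reading is that the theatre FBC fills in when no routine one exists. The share affected could be small, and the bias shrinks in proportion. This stands, and it is why the bias is written as share times fall.

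**No Hb rise at issue is defined.** It is tempting to say that dilution could hide the very effect the study looks for. But 0.47 g/dL is a between-group difference from an adult intravenous-iron trial, while this is a within-child study of oral iron whose power calculations are in SD units. If the true rise is nearer 1.0 g/dL, significance is little threatened. This stands as well, so 0.47 g/dL serves only as a yardstick.

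**The fall is wholly assumed.** The documents give no fluid volume, retained fraction or blood volume, and a draw before fluid has no dilution component. This stands: the range starts at zero.

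**The problem might be repairable afterwards.** One might infer that the dilution could never be removed. That is not established. Section 6.13 is not exhaustive (adherence and adverse events are collected but not listed there), the content of the Surgical Admission CRF (Appendix G) is not shown, and section 6.12 lets sites supply missing data points. Still, neither the listed dataset nor the analysis plan makes use of any such record.

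**The net shift need not always be downwards.** Dilution lowers Hb, but effects of posture, anaesthesia or a preoperative fluid deficit are not quantified in the documents. The claim about direction is therefore limited to the fluid component.

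**Conclusion.** The concern holds in a limited form. The documents leave open which FBC supplies the post-iron half of the primary outcome, set no condition on fluid before the theatre draw, list no field for source or prior fluid, and plan no analysis that accounts for either. In an uncontrolled pre-post design, dilution in the affected children would bias DHb against showing a rise.

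The size is unknown. Under the stated assumptions, the fall per affected child runs from zero to 0.48 g/dL at 5 mL/kg and to 0.91 g/dL at 10 mL/kg; the bias in the mean is that fall times an unstated share. This does not show that the study will miss an iron effect. It shows that a modest rise could be understated without the listed data revealing it. Because the remedy is cheap, the change should be made.

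**What to change.** 1. In section 6.12, name the endpoint FBC: the awake FBC from the same admission where one exists, otherwise the theatre sample. State that the theatre FBC is taken whenever no such awake result is available.
2. In section 6.12, specify that the theatre tubes are drawn at cannula insertion, before any intravenous fluid. This is a rule about when the sample is taken, not about fluid management.
3. Add to section 6.13 and to the Surgical Admission CRF the source of the sample and any fluid given before the draw (mL/kg). Section 6.14 has that form completed by the surgical team on admission, so this entry has to be made later, in theatre.
4. In section 5.11, add a sensitivity analysis of DHb by sample source. Read it with care, because children with and without routine bloods may differ in other ways.

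**Cost.** The theatre draw and tubes are those already planned, and no extra needle is needed. Someone must take the tubes at cannulation and make one CRF entry in theatre. Any effect of posture or of anaesthesia itself would remain; the analysis by source would help to show it but would not remove it.
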